7.4.5.1. Liver Chemistry Stopping and Follow-up Criteria

Liver chemistry threshold stopping criteria have been designed to assure participant safety and to evaluate liver event etiology during administration of study drug and the follow-up phase. All Phase 3 participants who meet liver stopping criteria will be adjudicated by the ViiV Safety and Labelling Committee (VSLC) – resulting in a case summary, adjudication, and management plan. The VSLC contains an external expert hepatologist, familiar with both DILI and cabotegravir, who will participate in this review. This committee meets on a 3-weekly basis, and can be convened on an ad hoc basis as needed.

7.4.5.2. Diarrhea

Participants with Grade 1 or 2 diarrhea may continue study treatment without interruption. Participants with diarrhea of any toxicity grade may be treated symptomatically with anti-motility agents; however, the recommended daily dose of the chosen anti-motility agent must not be exceeded. If symptoms persist or get worse on the recommended daily dose of the chosen anti-motility agent then the anti-motility agent must be discontinued and consultation made with the Medical Monitor.

For participants with Grade ≥ 3 diarrhea that is unresponsive to the recommended dose of the anti-motility agents and for which an alternative etiology (e.g., infectious diarrhea) is not established, the treatment with the anti-motility agent and IP must be interrupted until resolution of diarrhea to Grade ≤ 2 or Baseline, after which IP and background ART may be resumed after discussion and agreement with the Medical Monitor. If Grade ≥ 3 diarrhea recurs within 28 days upon the resumption of IP, the IP should be permanently discontinued and the participant withdrawn from the study. Any participant receiving at least one dose of CAB LA and /or RPV LA who discontinue IP / Withdraw will initiate treatment with HAART and enter the LTFU Phase for 52 weeks of follow up.

If loperamide is used for treatment of diarrhea, local prescribing information should be followed with respect to dose and frequency of administration. Loperamide dosing should not exceed local prescribing information.

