- Participants who are not eligible to continue into the Maintenance Phase.
- Participants who are not eligible, or do not wish to continue on to the Extension Phase.
- Virologic withdrawal criteria as specified in Section 5.5.4 are met;
- Participant requires substitution of ART;
- Participant requires substitution or dose reduction of CAB LA or RPV LA (oral bridging supply and potential for a second loading dose may be permissible following discussion with the Medical Monitor).
- Liver toxicity where stopping criteria are met and no compelling alternate cause is identified (see Section 5.5.1);
- Renal toxicity are met and no compelling alternate cause is identified;
- QT interval (QTc) interval >550 msec from three or more tracings separated by at least 5 minutes and considered causally related to IP.
- Grade 4 clinical AE considered causally related to study drug;
- Participant has a Grade 3 or higher rash or Grade 2 rash with evidence of systemic involvement and no compelling alternative cause is identified
- Pregnancy (intrauterine), regardless of termination status of pregnancy.
- Participant withdrew consent

Efficacy data for participants withdrawing from the study will be considered evaluable up to the point at which they are withdrawn using the same criteria for evaluability as for participants who complete the study.

Safety data for all participants who receive any amount of study drug, including participants who withdraw from the study, will be included in evaluations of safety.

All data from the Withdrawal visit will be recorded, as they comprise an essential evaluation that should be done prior to discharging any participant from the study.

The following actions must be taken in relation to a participant who fails to attend the clinic for a required study visit:

- a. The site must attempt to contact the participant and re-schedule the missed visit as soon as possible.

- b. The site must counsel the participant on the importance of maintaining the assigned visit schedule and ascertain whether or not the participant wishes to and/or should continue in the study.

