6.9.1. IM Dosing

Participants receiving CAB LA and/or RPV LA are anticipated to be at risk for development of virologic resistance if ART is interrupted. The time period during which participants are at risk for development of virologic resistance may be determined by the period between when drug levels fall below therapeutic values and when they fall below levels which exert selective pressure on HIV. This time period will vary by ART agent and is dependent upon effective concentration, inhibitory concentration, and half-life.

Plasma concentrations of both LA drugs may be measurable for more than one year following IM injections. Any interruption in IM dosing should be discussed with the Medical Monitor. Investigators should ensure that the participant initiates alternative highly active ART to minimize the risk of developing resistance as concentrations of CAB and RPV decline over time.

IM dosing is expected to occur during the week in which the participant's projected visit falls (as according to the date of the first injection). The first injections for participants from ATLAS on CAB LA + RPV LA Q4W will occur at Day 1. The first injections for participants transitioning from oral SOC are administered at Week 4b (can be performed as soon as lab results from Week 4a become available and should be performed where possible within 2 weeks of visit 4a), and the second injections are given at Week 8. Between the Week 4a and 4b visits, participants must continue daily treatment with oral CAB and RPV tablets.

Since the first injection visit (Day 1 or 4b) will determine the future injection visit schedule for participants, planning for the first injection visit date (within allowed visit windows) should take into consideration the availability of the participants to adhere to future visit windows (planned vacations, business trips, *etc.*).

CAB LA + RPV LA dosing for participants transitioning from SOC treatment is as follows:

All injections should be planned as single injections per drug.

6.9.1.1. IM injections every 4 weeks (Q4W):

Week 4b only - CAB LA 600 mg + RPV LA 900 mg, each given as 1 X 3 mL IM injection

Week 8 and Q4W thereafter - CAB LA 400 mg IM + RPV LA 600 mg IM every 4 weeks for 100 weeks, each given as 1 X 2 mL IM injection

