7.4.4.3. Grade 3 Toxicity/Adverse Event

Participants who develop a Grade 3 AE or toxicity should be managed as follows:

- If the Investigator has compelling evidence that the Grade 3 AE or toxicity has not been caused by IP, dosing may continue after discussion with the Medical Monitor.
- Participants who develop a Grade 3 AE or toxicity, which the Investigator considers related or possibly related to the IP, should have the IP withheld and be rechecked each week until the AE returns to Grade 2. Once the AE is Grade \leq 2, IP may be re-started.
- Should the same Grade 3 AE recur within 28 days in the same participant, the IP should be permanently discontinued and the participant withdrawn from study.
- Participants experiencing Grade 3 AEs requiring permanent discontinuation of IP should be followed weekly until resolution of the AE and to have withdrawal study evaluations completed. A follow-up visit should be performed 4 weeks after the last dose of IP. Any participant receiving at least one dose of CAB LA and /or RPV LA who discontinue IP / Withdraw will initiate treatment with HAART and enter the LTFU Phase for 52 weeks of follow up.

- Participants with Grade 3 asymptomatic laboratory abnormalities should be investigated for all potential non-drug related causes, and, following discussion with the Medical Monitor, may continue IP if the Investigator has compelling evidence that the toxicity is not related to IP, with the exception of liver chemistry stopping criteria (See Section 7.4.5.1). Isolated Grade 3 lipid abnormalities do not require withdrawal of IP.

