7.4.4.4. Grade 4 Toxicity/Adverse Event

- Participants who develop a Grade 4 AE or toxicity must have IP permanently discontinued. However, if the Investigator has compelling evidence that the AE is not causally related to the IP, dosing may continue after discussion with, and assent from, the Medical Monitor. Participants should be rechecked each week until the AE returns to Grade 2.
- Participants experiencing Grade 4 AEs requiring permanent discontinuation of IP should be followed weekly until resolution of the AE and encouraged to complete the withdrawal and follow-up study evaluations as noted above. Any participant receiving at least one dose of CAB LA and /or RPV LA who discontinue IP / Withdraw will initiate treatment with HAART and enter the LTFU Phase for 52 weeks of follow up.
- Participants with Grade 4 asymptomatic laboratory abnormalities should be investigated for all potential non-drug related causes, and, following discussion with the Medical Monitor, may continue therapy if the Investigator has compelling evidence that the toxicity is not related to IP, with the exception of liver chemistry stopping criteria (See Section 7.4.5.1). An in-clinic follow-up visit will be performed approximately 4 weeks after the last dose of study medication if AEs, SAEs, or laboratory abnormalities considered potentially harmful to the participant are ongoing at the last on-study visit. Isolated Grade 4 lipid abnormalities do not require withdrawal of IP.

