Lipohypertrophy ⁵	Detectable by study participant, caregiver, or physician AND Causing no or minimal interference with usual social & functional activities	Obvious on visual inspection AND Causing greater than minimal interference with usual social & functional activities	Disfiguring changes	NA

⁵ Definition: A disorder characterized by abnormal fat accumulation on the back of the neck, breasts, and abdomen.

Gastrointestinal

PARAMETER	GRADE 1 MILD	GRADE 2 MODERATE	GRADE 3 SEVERE	GRADE 4 POTENTIALLY LIFE- THREATENING
Anorexia	Loss of appetite without decreased oral intake	Loss of appetite associated with decreased oral intake without significant weight loss	Loss of appetite associated with significant weight loss	Life-threatening consequences OR Aggressive intervention indicated (e.g., tube feeding, total parenteral nutrition)
Ascites	No symptoms	Symptoms AND Intervention indicated (e.g., diuretics, therapeutic paracentesis)	Symptoms recur or persist despite intervention	Life-threatening consequences
Bloating or Distension Report only one	Symptoms causing no or minimal interference with usual social & functional activities	Symptoms causing greater than minimal interference with usual social & functional activities	Symptoms causing inability to perform usual social & functional activities	NA
Cholecystitis	NA	Symptoms AND Medical intervention indicated	Radiologic, endoscopic, or operative intervention indicated	Life-threatening consequences (e.g., sepsis, perforation)
Constipation	NA	Persistent constipation requiring regular use of dietary modifications, laxatives, or enemas	Obstipation with manual evacuation indicated	Life-threatening consequences (e.g., obstruction)
Diarrhea ≥ 1 year of age	Transient or intermittent episodes of unformed stools OR Increase of ≤ 3 stools over baseline per 24-hour period	Persistent episodes of unformed to watery stools OR Increase of 4 to 6 stools over baseline per 24-hour period	Increase of ≥ 7 stools per 24-hour period OR IV fluid replacement indicated	Life-threatening consequences (e.g., hypotensive shock)
< 1 year of age	Liquid stools (more unformed than usual) but usual number of stools	Liquid stools with increased number of stools OR Mild dehydration	Liquid stools with moderate dehydration	Life-threatening consequences (e.g., liquid stools resulting in severe dehydration, hypotensive shock)

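### Section 7.4.5.2 allows study drug to be resumed after unexplained Grade 4 diarrhoea, where Section 7.4.4.4 requires a permanent stop

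*Protocol*

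**What the plan says.** Four parts of the protocol bear on a participant with Grade 4 diarrhoea.

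- **Section 7.4.5.2 (Diarrhea).** The rule opens: "For participants with Grade ≥ 3 diarrhea that is unresponsive to the recommended dose of the anti-motility agents and for which an alternative etiology" has not been established. IP is held until the diarrhoea falls to Grade 2 or lower, or to Baseline, "after which IP and background ART may be resumed after discussion and agreement with the Medical Monitor". Permanent discontinuation follows only if diarrhoea of Grade 3 or higher returns within 28 days of resuming.
- **Section 7.4.4.4 (Grade 4 Toxicity/Adverse Event).** "Participants who develop a Grade 4 AE or toxicity must have IP permanently discontinued". Dosing may continue only "if the Investigator has compelling evidence that the AE is not causally related to the IP", and then only after discussion with the Medical Monitor and with the Monitor's assent. Isolated Grade 4 lipid abnormalities are exempted by name. Diarrhoea is not.
- **Section 5.5 (Withdrawal/Stopping Criteria).** The reasons for mandatory discontinuation include "Grade 4 clinical AE considered causally related to study drug".
- **Appendix 2 (DAIDS table, Gastrointestinal).** From one year of age, Grade 4 diarrhoea is defined by "Life-threatening consequences (e.g., hypotensive shock").

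**The concern.** Grade 3 or higher takes in Grade 4. For a life-threatening episode with no identified cause, Section 7.4.5.2 opens a route to re-dosing, while Section 7.4.4.4 requires a permanent stop in almost any such case. A site or Medical Monitor could follow either section and believe the protocol was being observed.

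Participant safety and a single, consistent stopping rule are at stake. A long-acting injection cannot be withdrawn once given, and Section 6.9.1 states: "Plasma concentrations of both LA drugs may be measurable for more than one year following IM injections". A decision to re-dose after an unexplained life-threatening event is therefore hard to undo.

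**Working it through.** No figure is involved, so the check is a comparison of text. Take one participant with Grade 4 diarrhoea, unresponsive to anti-motility agents, with no alternative cause established.

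| Question | Section 7.4.5.2 | Section 7.4.4.4 |
|---|---|---|
| Does the section apply? | Yes: Grade 3 or higher includes Grade 4 | Yes: any Grade 4 AE or toxicity |
| First action | Interrupt IP | Discontinue IP permanently |
| Condition for further dosing | Grade 2 or lower (or Baseline) and Medical Monitor agreement | Compelling evidence of no causal relation, and Medical Monitor assent |
| When is the stop permanent? | Second episode of Grade 3 or higher within 28 days of resuming | First Grade 4 episode, unless the exception is met |

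1. **Is the Grade 4 exception available?** Section 7.4.5.2 applies when no other cause has been established. Without one, an investigator would not normally hold compelling evidence that IP was not responsible. The exception would ordinarily fail, and the two sections give different answers for the same person.

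2. **Is there a conflict at Grade 3?** No. Section 7.4.4.3 withholds IP for a related or possibly related Grade 3 event and allows re-start once it is Grade 2 or lower. It then adds: "Should the same Grade 3 AE recur within 28 days in the same participant, the IP should be permanently discontinued". Section 7.4.5.2 follows the same sequence with the grade widened from 3 to 3 or higher. The conflict comes from that widening.

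3. **Does Section 5.5 settle it?** Only in part. Its trigger is a Grade 4 clinical AE considered causally related. That is narrower than Section 7.4.4.4, which stops IP unless non-causality is strongly supported. An event of uncertain cause falls between the two.

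4. **Does the protocol rank the sections?** No. Section 7.4.5 introduces its content as general guidelines and claims no precedence over Section 7.4.4. The lipid exemption shows how an intended exception was handled: it appears in both Section 7.4.4.4 and Section 7.4.5.3.

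5. **How are other clinical events treated?** By the stricter standard.
   - Section 7.4.5.6 allows re-challenge after possibly or probably related pancreatitis only on compelling evidence that IP was not the cause.
   - Section 7.4.5.11 requires permanent discontinuation for allergic reactions of Grade 3 or higher that are possibly or probably related.
   - Section 7.4.5.13 requires it for isolated Grade 3 or 4 rash unless study drug has been definitively ruled out as the cause.

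6. **Is the wording adapted to this trial?** The sentence speaks of resuming background ART, although CAB plus RPV is the whole regimen here. This is consistent with text carried over unadapted, but that is inference and the finding does not depend on it.

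**The case against.** The best case for leaving the text alone has four parts.

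- **The two rules can be obeyed together.** Section 7.4.5.2 says IP may be resumed; it does not direct re-dosing or switch off other stopping rules. A Grade 4 event considered related is stopped under Section 5.5 in any case. This stands as far as it goes, and it narrows the gap to Grade 4 events neither considered related nor shown to be unrelated. Section 7.4.4.4 requires a stop in that group and Section 7.4.5.2 does not.

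- **The specific rule may be meant to override the general one.** Other parts of Section 7.4.5 set their own paths at Grade 4: lipase (7.4.5.6), CPK (7.4.5.5) and a fall in estimated GFR of more than 50% (7.4.5.7). This weakens any argument from the lipid exemption alone. But these are laboratory findings, not a life-threatening clinical event, and nothing in the text states the precedence.

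- **The Medical Monitor is a safeguard.** The site cannot resume alone. That is true, and resumption is not automatic. But Section 7.4.4.4 requires the Monitor's assent as well as the evidence. Section 7.4.5.2 keeps the agreement and omits the evidential test.

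- **A cause may be found during the interruption.** It may, and then Section 7.4.4.4 would allow dosing to continue. Section 7.4.5.2 does not make resumption depend on it.

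Two further points are fair. The sentence on drug persistence in Section 6.9.1 was written about resistance, not toxicity; it is used here only for how long exposure can last. The scenario is also remote: the risk tables in Section 2.3.1 do not list diarrhoea as a risk of clinical significance for CAB or RPV LA.

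**Conclusion.** The concern holds. For Grade 4 diarrhoea that is unresponsive to treatment and unexplained, Section 7.4.5.2 permits what Section 7.4.4.4 forbids, and the protocol does not say which governs. The direct conflict is with Section 7.4.4.4; Section 5.5 is supporting. There is none at Grade 3.

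The protocol gives no count of Grade 4 diarrhoea, so no rate is offered; the event is expected to be rare. For a participant affected, the difference is a permanent stop at the first Grade 4 episode against a stop only at a second episode of Grade 3 or higher within 28 days of resuming. No effect is claimed on the Snapshot endpoint, the tolerability comparison, sample size, power or type I error.

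The conclusion rests on two readings: that Grade 3 or higher means what it says, and that absence of an established alternative cause does not ordinarily amount to compelling evidence of non-causality. The text should be changed on grounds of participant safety and consistency.

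**What to change.** In Section 7.4.5.2, restrict the interrupt-and-resume sentence to Grade 3 diarrhoea. Add that Grade 4 diarrhoea is managed under Sections 7.4.4.4 and 5.5. The recurrence sentence can stay at Grade 3 or higher, since a Grade 4 recurrence should also end treatment.

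The cost is one changed sentence and one cross-reference in an amendment. Sample size, visits and analysis are unaffected.

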7.4.5.3. Hypertriglyceridemia/ Hypercholesterolemia

Samples for lipid measurements **must** be obtained in a fasted state according to the Time and Events table (Section 7.1). Participants who experience asymptomatic triglyceride or cholesterol elevations may continue to receive IP. Clinical management of participants with hypertriglyceridemia/hypercholesterolemia should **not** be based upon non-fasting samples (obtained in the fed state). A confirmatory fasting triglyceride and/or cholesterol level should be obtained prior to the institution of medical therapy for hyperlipidemia. Isolated Grade 3 and Grade 4 lipid abnormalities do not require withdrawal of IP.

Please see the Recommendations of the Adult AIDS Clinical Trial Group Cardiovascular Disease Focus Group [[Dube, 2003](#)] for full discussion of management of hyperlipidemia in the context of HIV therapy.

7.4.5.4. Seizures

Three cases of seizures have occurred in the CAB program cumulatively through 01 October 2015.

ViiV Healthcare has reviewed these cases in detail and does not believe they constitute a reasonable likelihood of causation associated with CAB. This assessment is supported by the lack of preclinical signal, class effect or known CNS mechanism, the relatively low frequency of seizures relative to expected rates in both healthy and HIV positive participants and clinical confounders in each case. The Sponsor considers the risk of developing seizures on the study as being no higher than that of the rest of the HIV-1 infected population.

Seizures that occur on study should be managed according to the local guidelines on emergency seizure management which may include treatment with benzodiazepines, general supportive treatment, exclusion of metabolic and toxicological abnormalities using laboratory tests, septic workup and excluding underlying structural abnormalities with neuroimaging.

Where seizures occur, the Sponsor would like to better characterize these occurrences to enable systematic analyses.

Investigators are requested to document and report seizure or possible seizure events promptly (within 24 hours of learning of the event) to the Sponsor for evaluation and onward reporting. Data should be documented on the appropriate eCRF seizure page.

7.4.5.5. Creatine Phosphokinase (CPK) Elevation

A Grade 3 or higher elevation in CPK should result in a repeat assessment within 2-4 weeks to ensure the result is transient or due to exercise and will not require a change in study treatment. A history regarding use of drugs known to cause increase of CPK (such as statins) physical activity or exercise preceding the CPK evaluation should be obtained.

Grade 4 elevations in CPK should have a repeat assessment after the participant has abstained from exercise for >24 hours. For persistent Grade 4 CPK elevations that are considered possibly or probably related to the IP, IP should be discontinued and the participant withdrawn from the study. Any participant receiving at least one dose of CAB LA and /or RPV LA who discontinue IP / Withdraw will initiate treatment with HAART enter the LTFU Phase for 52 weeks of follow-up.

7.4.5.6. Lipase Elevations and Pancreatitis

Participants with asymptomatic Grade 1 or 2 elevations in lipase may be followed closely for the development of symptoms.

Participants with asymptomatic Grade ≥ 3 elevations in lipase that are considered possibly or probably related to IP should have IP interrupted until serum lipase returns to Grade ≤ 2 . The lipase assay should be repeated within 2 weeks of any Grade ≥ 3 result. Participants with persistence of Grade ≥ 3 lipase in the absence of other diagnoses or reoccurrence of lipase elevation (at Grade ≥ 2) following reintroduction of IP should permanently discontinue IP.

Participants with a confirmed diagnosis of clinical pancreatitis that is considered possibly or probably related to IP should have IP held. After complete resolution of the episode, participants may be re-challenged with IP after discussion with the Medical Monitor, only if the Investigator has compelling evidence that the event was not caused by IP. Upon re-challenge, lipase determinations should be performed every 2 weeks for at least 6 weeks after re-initiation of treatment. With any elevation of lipase of Grade ≥ 2 or any recurrence of symptoms, the participant should discontinue IP and be withdrawn from study.

Any participant receiving at least one dose of CAB LA and /or RPV LA who discontinue IP / Withdraw will initiate treatment with HAART and enter the LTFU Phase for 52 weeks of **follow up**.

Drug Restart Following Transient Resolving Liver Events Not Related to Study Drug

Approval by VSLC for drug restart can be considered where:

Liver chemistries have a clear underlying cause (e.g., biliary obstruction, hypotension, and liver chemistries have improved to normal or are within $1.5 \times$ baseline and $ALT < 3 \times ULN$). Ethics Committee or IRB approval of drug restart must be obtained, as required.

If restart of drug is approved by VSLC in writing, the participant must be provided with a clear description of the possible benefits and risks of drug administration, including the possibility of recurrent, more severe liver injury or death.

The participant must also provide signed informed consent specifically for the restart. Documentation of informed consent must be recorded in the study chart.

Study drug must be administered at the dose specified by VSLC.

Participants approved by VSLC for restarting study drug must return to the clinic once a week for liver chemistry tests for a minimum of one month and thereafter for as long as clinically indicated and then laboratory monitoring may resume as per protocol. If protocol defined stopping criteria for liver chemistry elevations are met, study drug must be stopped.

Refer to Section 11.2, U.S. Department of Health and Human Services, National Institutes of Health, National Institute of Allergy and Infectious Diseases, Division of AIDS. Division of AIDS (DAIDS) Table for Grading the Severity of Adult and Pediatric Adverse Events, Version 2.1. [March 2017]. Available from: <https://rsc.tech-res.com/docs/default-source/safety/daids-ae-grading-table-mar2017.pdf>

Refer to Section 11.3, Appendix 3: Liver Safety – Study Treatment Restart Guidelines for further details.

